Evaluation of Nicotinamide Riboside in Prevention of Small Fiber Axon Degeneration and Promotion of Nerve Regeneration

NCT03912220

Study Protocol including statistical analysis

Document Date: 01/16/2020

JHM IRB - eForm A – Protocol

- Use the section headings to write the JHM IRB eForm A, inserting the appropriate material in each. If a section is not applicable, leave heading in and insert N/A.
- When submitting JHM IRB eForm A (new or revised), enter the date submitted to the field at the top of JHM IRB eForm A.

1. Abstract

Small fiber neuropathy (SFN) is a type of peripheral neuropathy that affects the small unmyelinated fibers, including both somatic innervation of the skin and autonomic nerves. Although diabetes and prediabetes are the two most common causes, up to 50% of all SFN remain idiopathic. Currently there is no effective treatment that prevents it or reverses it through regeneration of nerve fibers.

Recent advances in understanding the molecular machinery that mediates Wallerian degeneration (i.e. degeneration of nerve fibers after physical transection) showed that key players in this pathway (e.g. NMNAT2, Sarm1) and NAD⁺ metabolites play a similar role in degeneration of axons in a distal-to-proximal manner seen in many peripheral neuropathies including SFN. Pre-clinical studies have shown that rapid depletion of NAD initiates a cascade of molecular events that leads to axon degeneration and that supplementation of a NAD precursor, nicotinamide riboside (NR) can prevent this degeneration.

In this study we plan to evaluate the ability of NR to prevent degeneration of small somatic sensory axons innervating the epidermis as well as its ability to promote regeneration of these same fibers in a human experimental model of nerve degeneration and regeneration. This experimental human model has been used previously to evaluate the rate of nerve degeneration and regeneration in several peripheral neuropathies and in healthy subjects.

Since NR is available as a nutritional supplement, if successful, this research can lead to development of a therapy for a variety of peripheral neuropathies very rapidly.

2. Objectives (include all primary and secondary objectives)

We propose to use an established model of capsaicin-induced axonal degeneration and regeneration to assess the potential of nicotinamide riboside (NR) to delay small unmyelinated nerve fiber degeneration as well as to promote regeneration. The study will test two hypotheses:

- (1) NR-treatment will reduce capsaicin-induced axonal degeneration in the epidermis in healthy controls.
- (2) NR-treatment will enhance axonal regeneration after capsaicin-induced epidermal denervation in healthy controls.

3. Background

Small fiber neuropathy (SFN) manifests in a variety of different diseases and often results in symptoms of burning pain, shooting pain, allodynia, and hyperesthesia (Tavee and Zhou, 2009). Although strength remains preserved in patients with SFN, the pain and paresthesia's are often disabling. Diabetes mellitus (DM) and impaired glucose tolerance (IGT) in combination with metabolic disease are the most common identified causes of SFN (Hovaguimian and Gibbons, 2011). In these cases, besides strict glucose control, no other treatment option has demonstrated the ability to slow or prevent axon loss in people with diabetic patients with peripheral neuropathy.

Pathologically, the peripheral nerve damage in patients with SFN affects predominantly or exclusively the small myelinated (A δ) fibers or unmyelinated C fibers. Many small fiber neuropathy patients test normally on conventional electrophysiological tests because intraepidermal nerve fiber function is not assessed by routine nerve conduction studies. Thus, in many patients, the only objective evidence of neuropathy is by skin biopsy determining the intraepidermal nerve fiber density (IENFD) in the collected skin tissue samples (Holland et al., 1998),

The capsaicin cream is an FDA approved medication available over the counter for treatment of various conditions including arthritis related joint pain and post herpetic neuralgia (Fernandes et al., 2016). It is the active ingredient in hot chili peppers and has been shown to bind vanilloid receptors on C- and A-delta nerve fibers leading to calcium entry and subsequent axonal degeneration (Marsh et al., 1987; Pini et al., 1990). The application of over-the-counter strength capsaicin cream (0.1%) for 48 hours leads to loss of intraepidermal nerve fibers mimicking the changes seen in small fiber neuropathies (Simone et al., 1998; Nolano et al., 1999). Associated with the loss of intraepidermal nerve fibers is a decrease in sensation in the area of the patch. Over weeks to months, the fibers slowly regenerate, repopulating the treated area ([name] et al., 2004; Hahn et al., 2007). This regenerative response is associated with improved sensory function as well.

[figure not shown]
Nicotinamide riboside (NR) is a pyridine-nucleoside form of vitamin B3 that functions as a precursor to nicotinamide adenine dinucleotide or NAD⁺. Studies in mice have shown that boosting the levels of NAD⁺ can produce multiple health benefits, including reducing nerve damage (Trammell et al., 2016a; Hamity et al., 2017). In humans, the levels of NAD⁺ diminish with age and it has been suggested that loss of this metabolite may play a role in age-related health decline (Johnson and Imai, 2018). NR is FDA approved as a dietary supplement and can be purchased over the counter.

4. Study Procedures

a. Study design:

This is a randomized double-blinded study to evaluate the effects of NR on experimental axon degeneration and regeneration. After the initial screening (visit 1) is completed, the patients will undergo a skin biopsy and be randomized to either the study drug or placebo and will be instructed to take it for a week prior to visit 2. Based on existing pharmacokinetic studies, this should be sufficient to raise the plasma NAD levels at the time of experimental denervation of the skin. At visit 2, patients will undergo two baseline skin biopsies and application of the capsaicin patch for 48 hours and will be instructed to continue the study drug. At visit 3 (48 hours after visit 2), capsaicin patch will be removed, and a repeat skin biopsy will be done to evaluate the degree of epidermal denervation. Patients will be instructed to continue the study drug for another 3 months and will undergo repeat skin biopsies at 2 months (visit 4) and 3

months (visit 5). Blood samples will also be drawn at each visit to measure NAD levels to confirm compliance and to correlate with degree of epidermal innervation. Figure 1 depicts a schema of visits and timelines.

b. *Study duration and number of study visits required of research participants.*

As outlined above, there will be a total of 5 visits over 3 and ½ months.

c. *Blinding, including justification for blinding or not blinding the trial, if applicable.*

The study will be done in a blinded manner where the clinical evaluation and the histopathological evaluation of degeneration and regeneration will be done by different teams. Patients will be randomized and given unique patient identifiers by the research coordinators. The staff at the cutaneous nerve laboratory carrying out the histopathological evaluation will not know the identities of the patients or the samples. At the end of the study, the code will be broken and the PI will have access to the histopathological evaluations and patient identities to carry out the statistical analysis.

d. *Justification of why participants will not receive routine care or will have current therapy stopped.*

The patients will continue with their current routine care. They will not be asked to stop any medication or care.

e. *Justification for inclusion of a placebo or non-treatment group.*

Since human nerves degenerate and regenerate at different rates, in order to find out if NR has any therapeutic value, we do need to include a placebo control group.

f. *Definition of treatment failure or participant removal criteria.*

No participant will be removed from the study. Even if the treatment does not lead to faster nerve regeneration, previous research has shown that after topical capsaicin, epidermis fully reinnervates within 6 months. We will examine whether NR can speed this regeneration.

Date: March 25, 2019

Principal Investigator: [name]

Application Number: IRB00210072

- g. *Description of what happens to participants receiving therapy when study ends or if a participant's participation in the study ends prematurely.*

Once the study is completed, the participants will continue with their regular life and medical care. If a participant leaves the study early, the impact on epidermal reinnervation is minimal as it will regenerate.

5. Inclusion/Exclusion Criteria

Study will be conducted in healthy adult patients aged 18-65 without any symptoms, signs or risk factors of peripheral neuropathy.

Inclusion criteria

- Age: 18-65
- BMI<32
- Normal neurological examination defined as NIS \leq 2 (Neuropathy Impairment Score)

Exclusion criteria

- History of peripheral neuropathy
- Any peripheral neuropathy risk factor including diabetes, Vitamin B12 deficiency, HIV-infection, chronic kidney or hepatic disease, hypothyroidism, chemotherapy or other know neurotoxic exposure.
- Pregnancy
- Abnormal Labs: HIV, B12, HgA1c, Thyroid Stimulating Hormone (TSH), Complete Blood Count (CBC), Comprehensive Metabolic Panel (CMP)

6. Drugs/ Substances/ Devices

- a. *The rationale for choosing the drug and dose or for choosing the device to be used.*

As outlined in background section NR is commercially available as a nutritional supplement and has been evaluated in humans in a Phase 1 pharmacokinetic study (Trammell et al., 2016b). It is safe at the doses used in that study (100 mg, 300 mg and 1000 mg) over the course of 36 days with no significant side effects except 2 patients reporting flushing sensation. Since NR is able to elevate the NAD levels in plasma, we expect that this correlates with elevated tissue levels of NAD and able to prevent distal axonal degeneration of small unmyelinated fibers induced by capsaicin.

- b. *Justification and safety information if FDA approved drugs will be administered for non-FDA approved indications or if doses or routes of administration or participant populations are changed.*

NR is available over the counter as a nutritional supplement as a form of vitamin B3 and is sold under various brand names including Tru Niagen at a dose of 300 mg per capsule. It is FDA approved as a nutritional supplement and recommended daily dose is 15 mg. However, based on the study by Trammell and colleagues, effect of NR on NAD metabolism was best observed at the highest dose of 1000 mg/day. There were no significant side effects or toxicity at that dose over 36 days of observation. Furthermore, a more recent clinical trial of NR in obese men looked at the effects of NR on insulin sensitivity over 12 weeks and utilized a dose of 1000 mg twice a day without any significant side effects or drop out from the study (Dollerup et al., 2018). In this study there were increases in multiple NAD metabolites in the serum and urine with this dose. Given that both studies did not observe any side effects or toxicity doses above 1000 mg a day, and that the study by Dollerup and colleagues showed increases in NAD metabolites, we plan to use 1000 mg orally (four 250mg capsules) twice a day for convenience

Date: March 25, 2019

Principal Investigator: [name]

Application Number: IRB00210072

of dosing using the commercially available NR. The placebo capsules will be prepared by ChromaDex who is also supplying the study drug.

- c. *Justification and safety information if non-FDA approved drugs without an IND will be administered.*
Not applicable

7. Study Statistics

- a. *Primary outcome variable.*

We are testing whether NR will reduce axonal degeneration as well as promote regeneration. The primary outcome will be the measurement of epidermal nerve fiber counts.

- b. *Secondary outcome variables.*

Plasma NAD levels will be measured and correlated with primary outcome measure

- c. *Statistical plan including sample size justification and interim data analysis.*

Aim 1 focuses on the ability of NR to reduce or prevent nerve fiber degeneration in the capsaicin model. From past studies, we know that following topical capsaicin application, the epidermis is nearly completely denervated. A previous study of 66 healthy control subjects, the baseline intraepidermal nerve fiber density was 22.7 ± 10.1 fibers/mm ([name] et al., 2006). Following 2 days of topical capsaicin application, the post-capsaicin IENFD was 0.25 ± 0.04 fibers/mm (nearly 99% reduction in nerve fiber density).

We expect a very similar study subject profile in the current study. If that is true, 20 subjects/arm will have a power of 0.8 to detect a difference in post-capsaicin epidermal nerve fiber density between NR and placebo of as low as 0.035 fibers/mm. If our subjects show more variability (standard deviation of 0.06 instead of 0.04) we would still have a power of 80% to detect a difference of 0.055 fibers/mm. Therefore, we are confident that a sample of 20 subjects/group is sufficient to determine whether NR decreases axonal degeneration in our model.

Aim 2 focuses on the potential for NR to promote IENFD regrowth. Following denervation with topical capsaicin, epidermal nerve fibers re-innervate the epidermis in a predictable fashion. Biopsies taken at two and three months following denervation have higher IENFD, the rate of regrowth is determined by calculating the slope of the line of IEND against time. Across several studies, this rate of nerve fiber regrowth has been 0.18 ± 0.08 fibers/mm/day ([name] et al., 2004). A sample of 20 subjects/group will have a power of 0.8 to detect a 40% or greater change in nerve fiber regeneration. We will have a power of 0.6 to detect a 30% improvement in regeneration.

- d. *Early stopping rules.*

The study will be terminated early if the subjects experience any significant side effects. NR is produced as a supplement by a number of different manufacturers. There have been no side effects reported. Additionally, it was well tolerated in several published studies. Therefore we do not anticipate any toxicity. If a subject complains of side effects, the potential for any causation will be reviewed by Drs. [name] and [name] and reported to the IRB.

8. Risks

Date: March 25, 2019

Principal Investigator: [name]

Application Number: IRB00210072

a. *Medical risks, listing all procedures, their major and minor risks and expected frequency.*

The capsaicin denervation model and other study procedures have been successfully performed in numerous Johns Hopkins IRB-approved studies (including as part of six industry-sponsored multicenter clinical trials with over 600 subjects total. Therefore, we do not anticipate any complications.

Neurological exam: There are no risks associated with a neurological examination.

Capsaicin cream: Capsaicin is the active ingredient in hot peppers and may cause a local burning sensation to the area that it is applied. The degree of burning is generally less than mild sunburn. The affected area will become less sensitive to sensory stimuli due to local nerve fiber degeneration. With time the area should return to normal or near normal with subsequent nerve regeneration and reinnervation of the skin. We have obtained IRB approval for similar studies in the past (RPN00-10-25-01, RPN 99-11-02-01, NA_00010088 (multicenter trial), WIRB Pr. No.: 20060008 (multicenter trial)) and have a FDA exemption letter for the use of topical capsaicin. The study participants may use over-the-counter, non-steroidal pain medications to manage any pain associated with the use of capsaicin cream.

Skin biopsy testing requires taking a 3mm-punch biopsy. The affected areas are anesthetized with subcutaneous 1% lidocaine with epinephrine, and the site will be sterilely dressed after the procedure. No sutures are involved. The patients will receive instructions how to care for each biopsy site after the procedure. The risk of infection is estimated at 1:500 and is likely less in healthy subjects. Punch skin biopsy may result in a small scar that generally fades by one year.

b. *Steps taken to minimize the risks.*

The skin biopsies will be done under sterile conditions. Patients will be given clear instructions on how to care for the biopsy sites.

c. *Plan for reporting unanticipated problems or study deviations.*

If the patients experience any signs of infection at the site of biopsies, they will be asked to call the study coordinator and/or principal investigator. They will be seen in the clinic and appropriate medical care will be provided. Similarly, if the patients experience any side effects from the study drug, they will be asked to call the study coordinator and/or the principal investigator and report it.

d. *Legal risks such as the risks that would be associated with breach of confidentiality.*

In order to preserve participant confidentiality, all study participant records will be stored in a locked file cabinet located in the study coordinator's office. All subjects will be given a study-specific unique identifying number and this will be used to label study documents. Data spreadsheets will use deidentified subject study numbers and will be password protected and stored on the study coordinator's computer which is backed up regularly.

e. *Financial risks to the participants.*

There is no cost to participate in the study.

9. Benefits

Date: March 25, 2019

Principal Investigator: [name]

Application Number: IRB00210072

There is no direct benefit to subjects. We are testing the potential benefit of NR on human nerve degeneration and regeneration.

10. Payment and Remuneration

There will be no cost to study subjects to participate. Subjects will be paid \$100/session for each study visit (\$500 total) plus \$100 if they complete all 5 visits of the study. Each subject will be paid \$300 after the 3rd visit and the remaining \$300 at the completion of the 5th visit. If subjects decide not to continue with the study, they will be paid for the sessions they completed but they will not be eligible to receive the study completion bonus of \$100.

11. Costs

- a. There is no cost to participate in the study.

12. References

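### Plasma NAD, the only exposure measure described, is sampled with no set or recorded time since the last dose and correlated without using the pre-drug visit-1 value

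*Combined protocol and SAP*

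**What the plan says.** All references are to the combined protocol and SAP.

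- **Sampling (Section 4a):** "Blood samples will also be drawn at each visit to measure NAD levels to confirm compliance and to correlate with degree of epidermal innervation". No clock time, interval from the last capsules, or recording of either is given.
- **Secondary outcome (Section 7b):** the whole entry is "Plasma NAD levels will be measured and correlated with primary outcome measure". It names no scale, baseline, covariate or visit pairing, and does not say whether the arms are pooled.
- **Dosing (Section 6b):** "we plan to use 1000 mg orally (four 250mg capsules) twice a day".
- **Order of events (Section 4a):** after screening at visit 1, participants are to "be randomized to either the study drug or placebo and will be instructed to take it for a week prior to visit 2". Blood drawn at visit 1 therefore precedes study drug.
- **Age (Sections 3 and 5):** human NAD levels are said to "diminish with age and it has been suggested that loss of this metabolite may play a role in age-related health decline", and the trial enrols "healthy adult patients aged 18-65 without any symptoms, signs or risk factors of peripheral neuropathy".

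No pill count, diary or other measure of exposure or compliance is described.

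**The concern.** The rationale in Section 6a runs from NR to higher plasma NAD, from there to higher tissue NAD, and so to protected axons. The NAD correlation is the only planned analysis that tests exposure against nerve outcome. If either aim shows no difference between arms, readers will ask whether exposure was achieved and whether it tracked the outcome.

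Two features weaken the answer. First, with twice-daily dosing one NR participant may be sampled soon after the capsules and another near the end of the interval, and their values enter the correlation as if comparable. The compliance check has the same difficulty: a low value could mean missed capsules or a late draw. Second, on the protocol's own premise about age, a level taken on treatment mixes the person's starting point with the response to NR. The visit-1 sample could separate the two, but the plan does not use it.

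The features differ in urgency. The visit-1 value can still be brought in at analysis. A dose time that nobody wrote down cannot.

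**Working it through.** **The plan's own figures.** The documents state no power or precision for the NAD correlation, so there is nothing to reproduce for it. The sample size comes from Section 7c: "20 subjects/arm will have a power of 0.8 to detect a difference in post-capsaicin epidermal nerve fiber density". For the stated difference of 0.035 with SD 0.04, assuming a two-sided 5% test, I get power 0.79 (normal approximation) or 0.77 (t-test), in line with the stated 0.8. That calculation does not involve NAD.

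**Inputs from the documents.** Twice-daily dosing, taken as a 12-hour interval; 20 participants in the NR arm.

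**Assumptions, none given in the documents.**
- Plasma NAD in an NR participant is a constant baseline plus a rise that declines exponentially after each dose.
- The peak rise R is 0.5, 1 or 2 times baseline.
- The half-life h of the rise is 6, 12, 24 or 48 hours.
- Draws are uniform over 0 to 12 hours after a dose.
- The between-subject CV is 30%, treated as the true exposure signal.
- The true correlation is 0.5, tested two-sided at 5%, with one NAD value per person.

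**Formulas.**
1. Level at t hours, relative to baseline: 1 + R × 2^(−t/h).
2. Timing noise s_w: the SD of ln(1 + R × 2^(−t/h)) over t uniform on 0 to 12.
3. Between-subject SD on the log scale: s_b = √ln(1 + 0.30²) = 0.294.
4. Attenuation: s_b / √(s_b² + s_w²).
5. Power (Fisher z): Φ(atanh(r) × √(n − 3) − 1.96); the other tail is negligible.

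**Without timing noise.** atanh(0.5) × √17 = 0.549 × 4.123 = 2.265, and Φ(2.265 − 1.96) = 0.62. Even then, the smallest correlation detectable at 80% power in 20 participants is 0.59.

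**One case in full (R = 1, h = 6).** Peak is 2 and trough is 1 + 0.25 = 1.25, a ratio of 1.6. s_w = 0.136. Attenuation = 0.294 / √(0.294² + 0.136²) = 0.91. Observed r = 0.454, and power = Φ(0.490 × 4.123 − 1.96) = 0.52.

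**All cases: attenuation, with power in brackets.**

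| Half-life of the rise | R = 0.5 | R = 1 | R = 2 |
|---|---|---|---|
| 6 h | 0.96 (0.58) | 0.91 (0.52) | 0.83 (0.44) |
| 12 h | 0.98 (0.60) | 0.96 (0.58) | 0.93 (0.55) |
| 24 h | 0.99 (0.61) | 0.99 (0.61) | 0.98 (0.60) |
| 48 h | 1.00 (0.62) | 1.00 (0.62) | 0.99 (0.61) |

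Averaging two or three visits would reduce the loss further if the timing errors are independent between visits.

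**Matching samples to aims.** Visits 2 and 3 bracket the 48-hour patch period. Visits 3, 4 and 5 span regrowth. The samples needed for both aims are already collected; only the pairing rule is absent from Section 7b.

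**The case against.** **The effect may be negligible.** The documents give no profile of NAD within a dosing interval. If the rise lasts a day or more, timing costs almost nothing. This stands, and it is why the point is minor. It also favours recording the times, since they would let the sponsor show that the effect was small.

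**The loss could be read as far larger.** A reader might let the whole NAD level, not just the rise, decay between doses. At a 6-hour half-life that gives a peak-to-trough ratio of 4, attenuation 0.59 and power of about 0.24. It assumes NAD is zero without NR, which contradicts the protocol's own premise of an age-dependent natural level.

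**Silence is not a plan.** A reader might infer that blood will be drawn at random times, or that the protocol has chosen unadjusted levels. It says neither; timing and scale are unspecified. Visits could turn out to cluster at one time of day, and uniform draws are an assumption.

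**The absolute level is a legitimate exposure measure.** The rationale is that depletion starts degeneration and raised NAD protects, so the level reached may matter in itself. A log ratio to visit 1 would discard that information and add visit-1 assay error. This stands against requiring a ratio. Nor does the calculation show how much a baseline adjustment would gain, because it treats between-subject spread as signal.

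**Scope.** Time since dose adds no NR-related noise at visit 1 or in the placebo arm, and the plan does not confine the correlation to NR participants. The power figures apply only to an analysis within the NR arm.

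**Conclusion.** The point holds as a minor, cheap improvement to a secondary analysis. The plan neither fixes nor records time since dose for its only described exposure and compliance measure, and Section 7b leaves unused a pre-drug sample that the schedule already provides.

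The plausible cost of timing noise is small to moderate: the correlation keeps 0.83-0.96 of its true value at a 6-hour half-life, 0.93-0.98 at 12 hours, and at least 0.98 from 24 hours. These ranges rest on the assumed peak rise (0.5 to 2 times baseline), uniform draws and a 30% between-subject CV. The benefit of using visit-1 NAD rests on the protocol's statement about age and has not been quantified.

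A reader might infer that the trial's conclusions about NR are at risk. They are not: the randomized comparison of nerve fiber density and regrowth does not use NAD. A reader might also infer that no baseline NAD exists; under Section 4a it is drawn.

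**What to change.** **Section 4a.** Record the clock times of the last dose and of each NAD draw. Schedule each participant's visits 2 to 5 at a similar time of day where feasible. Do not change when capsules are taken: holding them until after the draw would alter dose timing around the capsaicin challenge.

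**Section 7b.** Analyse on-treatment NAD adjusted for visit-1 NAD and time since last dose, with age as a sensitivity covariate. Pair NAD at visits 2 and 3 with visit-3 IENFD for Aim 1, and NAD at visits 3 to 5 with the regrowth slope for Aim 2. State whether the analysis is within the NR arm or pooled.

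**Cost.** Two form fields, a few sentences of analysis text, slightly less scheduling flexibility, and one or two degrees of freedom in a small sample. Dose, visits and number of samples do not change.

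### The NAD correlation has no treatment-arm term, so over all subjects it can simply repeat the arm contrast; separately, current users of over-the-counter NR are not excluded

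*Combined protocol and SAP*

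**What the plan says.** **NAD analysis.** Section 7b states: "Plasma NAD levels will be measured and correlated with primary outcome measure". Section 4a adds: "Blood samples will also be drawn at each visit to measure NAD levels to confirm compliance and to correlate with degree of epidermal innervation". Neither section names an arm term, a within-arm analysis or a rule for reading the result. NAD is the only secondary outcome.

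**Expected arm differences.** Of the week of dosing before capsaicin, section 4a says "this should be sufficient to raise the plasma NAD levels at the time of experimental denervation of the skin". Section 6a says "Since NR is able to elevate the NAD levels in plasma, we expect that this correlates with elevated tissue levels of NAD". The second hypothesis in section 2 is that "NR-treatment will enhance axonal regeneration after capsaicin-induced epidermal denervation in healthy controls"; the first is that NR reduces degeneration. The plan therefore expects the arms to differ on both variables in the correlation.

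**Access to NR.** Section 3 says "NR is FDA approved as a dietary supplement and can be purchased over the counter", and section 6b describes it as "sold under various brand names including Tru Niagen at a dose of 300 mg per capsule". The exclusions in section 5 are a history of neuropathy, risk factors ("Any peripheral neuropathy risk factor including diabetes, Vitamin B12 deficiency, HIV-infection, chronic kidney or hepatic disease" and others), pregnancy and abnormal laboratory values. None concerns NR or other supplements. Section 4d says that participants will not have to stop any medication.

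**The concern.** When two variables both differ by arm, pooling the arms produces a correlation between them even if they are unrelated within each arm. A significant result over all subjects then has two readings: subjects with higher NAD do better, or the NR arm has higher NAD and also does better. The second repeats the randomised comparison and adds nothing about NAD. Because section 6a links the expected benefit to raised NAD, a positive correlation could easily be taken as support for that mechanism. Under section 4c the principal investigator runs the analysis after the code is broken, so an unspecified choice between an all-subject and a within-arm analysis could be made with arms and results in view.

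The second issue bears on the primary contrast. A placebo subject who already takes NR is partly treated, which pulls the arm difference towards zero.

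**Working it through.** **Inputs from section 7c.** 20 subjects per arm. Aim 1: difference 0.035, SD 0.04 fibers/mm. Aim 2: rate 0.18, SD 0.08 fibers/mm/day, with effects of 40% and 30%. The documents state no significance level, so two-sided 0.05 is assumed.

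**Standardised effects (d).**
- Aim 1: 0.035/0.04 = 0.875 SD
- Aim 2, 40%: 0.40 × 0.18/0.08 = 0.9 SD
- Aim 2, 30%: 0.30 × 0.18/0.08 = 0.675 SD

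**The plan's own power figures** (normal approximation / noncentral t):
- Aim 1: 0.790 / 0.769 against a stated 0.8
- Aim 2, 40%: 0.812 / 0.792 against a stated 0.8
- Aim 2, 30%: 0.569 / 0.548 against a stated 0.6

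The first two reproduce. The third comes out a little below the stated figure, but nothing here depends on it. The plan gives no figure for the NAD correlation.

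**Correlation caused by arm alone.** Let k be the arm shift in NAD in within-arm SDs. With no within-arm association and equal arms,

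r = (k·d/4) / √[(1 + k²/4)(1 + d²/4)].

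For k = 2 and d = 0.9: r = 0.45 / √(2 × 1.2025) = 0.29.

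**How often that is significant.** The documents give no NAD shift, so k = 0.5, 1, 2 and 3 is assumed. Simulation used normal data, 40,000 trials per cell and 20 per arm. The all-subject Pearson test has 38 df; the arm-adjusted test has 37 df.

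| True NR effect | k = 0.5 | k = 1 | k = 2 | k = 3 |
|---|---|---|---|---|
| 0.9 SD (40%) | 0.094 | 0.210 | 0.472 | 0.619 |
| 0.875 SD (Aim 1) | 0.090 | 0.198 | 0.448 | 0.600 |
| 0.675 SD (30%) | 0.076 | 0.144 | 0.301 | 0.400 |
| none | 0.050 | 0.049 | 0.050 | 0.049 |

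With arm in the model, the rate is 0.049 to 0.052 in all 16 cells.

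**What adjustment costs if NAD is the mechanism.** Suppose the whole effect runs through NAD, so that within-arm r = d/k. (At k = 0.5 this would need r = 1.8 or 1.35, which is impossible.) The share of trials that are significant is:

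| Effect | Test | k = 1 | k = 2 | k = 3 |
|---|---|---|---|---|
| 0.9 SD | arm-adjusted | 1.000 | 0.840 | 0.464 |
| 0.9 SD | all subjects | 1.000 | 0.987 | 0.925 |
| 0.675 SD | arm-adjusted | 0.999 | 0.565 | 0.281 |
| 0.675 SD | all subjects | 1.000 | 0.861 | 0.723 |

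When NR shifts NAD strongly, the adjusted test can therefore miss a real pathway.

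**Dilution by NR users in the placebo arm.** Let p be the share of placebo subjects using NR and f the fraction of the full effect they get, with the SD unchanged. Then d = 0.9 × (1 − p·f), and power is from the noncentral t. One 300 mg capsule a day against the trial's 2 × 1000 mg gives f = 300/2000 = 0.15 if effect is proportional to dose; f = 1 is the upper bound. The numbers of users are assumed.

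| Users among 20 | f = 0.15 | f = 1 |
|---|---|---|
| 0 | 0.792 | 0.792 |
| 1 | 0.786 | 0.750 |
| 2 | 0.780 | 0.704 |
| 4 | 0.767 | 0.602 |

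**The case against.** The plan never says the correlation is over all subjects, and it claims neither a within-arm relation nor mediation. The difficulty arises only if the arms are pooled, NR works, NR shifts NAD, and a reader draws the wrong inference. If NR changes both variables, the marginal correlation is truly non-zero, so rejecting zero is correct: the rates in the first table are power for a real marginal association. The NAD shift is assumed. NAD is also drawn at five visits and the outcome covers both post-capsaicin density and a regrowth slope, so an arm term alone does not fully define the analysis. On supplements, the dose-proportional loss is negligible. The upper bound needs users to get the full trial effect from their own capsules, although section 6b reports the NAD effect as clearest at the highest dose studied. The bias is towards the null.

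Much of this stands. The first-table rates should not be called false positives, the conditions are all needed, and visit and method remain open. But these points do not remove the gap: the one planned secondary analysis cannot, as written, distinguish its two readings, and an arm-adjusted result helps whichever visit is chosen. Bias towards the null still costs power in a trial of 20 per arm. NAD measured at each visit might reveal users, but no rule applies it to eligibility or analysis.

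**Conclusion.** Both parts hold. On NAD, the defect is an unspecified analysis, not a stated wrong one. Run over all subjects, at the effects the protocol plans for, the correlation would be significant in roughly 8% to 62% of trials with no within-arm association at all. That range rests on assumed NAD shifts of 0.5 to 3 SD, normal data and one NAD value and one outcome per subject. If NR does not change the outcome, there is no inflation. This limits what the NAD correlation can show and leaves the randomised comparison untouched.

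On supplements, the eligibility rules admit current NR users. The loss in power is unknown, and small if effect is proportional to dose. Both points merit a change because the remedies are cheap, not because the trial's main result is in doubt.

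**What to change.** Keep the section 7b correlation and add text such as:

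> The association will also be reported adjusted for treatment arm (within-arm), beside the correlation over all subjects. The all-subject correlation alone will not be read as evidence that subjects with higher NAD do better, and a null adjusted result will not be read as ruling out an effect through NAD.

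Separately, add current use of NR supplements to the section 5 exclusion criteria.

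The first change needs no new samples or visits. Its cost is the low power of the adjusted test when NAD shifts strongly, which is why it accompanies the stated correlation and does not replace it. The second may turn away a few volunteers and does not cover NR started after enrolment.
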